### 6.1.2 DOSING AND ADMINISTRATION

In regard to drug administration, participants will be required to take Epidiolex with food. Of note, symptoms of food selectivity and food refusal are seen frequently in ASD (65). Therefore, if caregivers report that their child has initial difficulties accepting the CBD, the study clinicians will work on increasing participant tolerance and acceptance of the CBD through the use of standard behavioral intervention strategies for up to one week. If the participant continues to reject the dose he/she was assigned after one week of trial initiation, he/she will be withdrawn from the study.

Related to dosing, in Part 1 of the study, we employed the BOIN design (66, 67) in the first five cohorts of this open trial to estimate the optimal dose. The BOIN design was selected because it is more flexible than the traditional 3+3 design and possesses superior operating characteristics that are comparable to those of the more complex model-based designs, such as the continual reassessment method (CRM) (68).

We defined a target response rate for the optimal dose is  $\phi = 0.60$  and a maximum sample size of 30. We enrolled and treated participants in cohorts of size 3. The trial design was implemented through the following three steps:

1. Participants in the first cohort were treated at Dose Level 2 (see Table 1).
2. To assign a dose to the next cohort of participants, we conducted dose escalation/de-escalation according to the rule displayed in Table 2, which minimizes the probability of incorrect dose assignment with response rates of  $\phi_1 = 0.684$  and  $\phi_2 = 0.52$  designated as the uncertainty interval. When using Table 2, please note the following:
  - a. "Eliminate" means that we eliminate the current dose from the trial to prevent treating any future participants at this dose because the response rate is too low.
  - b. When we eliminate a dose, automatically de-escalate the dose to the next lower level.
  - c. If none of the actions (i.e., escalation, de-escalation or elimination) is triggered, we treat the new participants at the current dose.
  - d. If the current dose is the lowest dose and the rule indicates dose de-escalation, treat the new participants at the lowest dose.
  - e. If the current dose is the highest dose and the rule indicates dose escalation, treat the new participants at the highest dose.
3. Repeat step 2 until the maximum sample size of 30 is reached.

**Table 1.** Dose levels

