Dose Level 1	Dose Level 2	Dose Level 3
3 mg/kg/day	6 mg/kg/day	9 mg/kg/day

**Table 2.** Dose escalation/de-escalation/elimination rules for the BOIN Design and results in the first 5 cohorts

Cohort	1	2	3	4	5	6	7	8	9	10
Number of participants treated at the current dose	3	6	9	12	15	18	21	24	27	30
Dose administered (mg/kg/d)	6	6	3	3	6	-	-	-	-	-
Cumulative N of respondents	1	3	4	4	5	-	-	-	-	-
Escalate if # of responses >=	3	5	7	9	11	13	15	17	19	21
Deescalate if # of responses <=	NA	3	4	6	7	9	10	12	14	15
Eliminate if # of responses <=	NA	1	2	4	5	7	8	10	12	13

For purposes of the study design, participants were categorized as either “responders” or “non-responders” at the end of the 6-week intervention phase in order to determine the dose level for the following cohort. This categorization was based upon the following procedures.

- After completing and meeting eligibility criteria, study staff (including child psychologists and psychiatrists with expertise in ASD and comorbid symptoms) met to consensus on an individualized, primary outcome variable for each participant at the enrollment/baseline visit. The primary target was what is most interfering in the child’s functioning at the time of assessment and chosen based upon informant report, scores from a battery of standardized assessments covering a wide range of core and associated symptom

- domains, and clinical observations. Clinician consensus also yielded a Clinical Global Impression-Severity (CGI-S) score to represent the study team's impression of the participant's current severity of illness.
- After the final study visit, study staff met again to consensus on the degree of improvement observed in the predetermined primary outcome variable for each child. A CGI-S score was also determined. Definitions of response and non-response are provided below.
    - Response: In the absence of dose limiting effects, a Clinical Global Impression Scale – Improvement (CGI-I) score of 1 (very much improved) or 2 (much improved) determined by consensus based upon clinical judgment, informant report, and change in scores on measures (using the Reliable Change Index when possible) relevant to the predetermined primary outcome.

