#### 9.4.1 GENERAL APPROACH

The primary aim of this study is to determine the optimal dose of CBD in children and adolescents with ASD. Therefore, to increase sensitivity in capturing a nonlinear dose response, we will employ the BOIN design as discussed above. After the trial is completed, we will select the optimal dose based on isotonic regression as specified in Liu and Yuan (66).

---

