#### 9.4.2 ANALYSIS OF THE PRIMARY EFFICACY ENDPOINT(S)

We will select as the optimal dose the dose for which the isotonic estimate of the response rate is closest to the target response rate. If there are ties, we will select the higher dose level when the isotonic estimate is lower than the target response rate and we will select the lower dose level when the isotonic estimate is greater than or equal to the target response rate.

As mentioned, response rate will be determined by the proportion of participants classified as responders. A treatment response is defined as a CGI-I score of 1 or 2 on the individualized, predetermined primary outcome variable, whereas a nonresponse is a CGI-I score of 3 or greater. Scores on the CGI-I will be determined by clinician consensus.

Table 5 shows the operating characteristics of a 5-dose BOIN design based on 1000 simulations. The operating characteristics show that the design selects the true optimal dose, if any, with high probability and allocates more participants to the dose levels with the response rate closest to the target of 0.6. Please refer to Tables 3 and 4 for the design and statistical expectations relevant to Part 2 of the study.

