**Table 5. Operating characteristics of the BOIN design: Part 1**

	Dose 1	Dose 2	Dose 3	Dose 4	Dose 5	# of Participants	% Early Stopping
True Response Rate	0.4	0.5	0.6	0.55	0.45		
Selection %	17.1	9.3	21.8	22.0	1.7		28.1
# Participants treated	5.84	4.39	10.55	5.36	0.86	27	

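### The isotonic dose-selection step has no stated direction, and read literally it can name 9 mg/kg/day optimal on a lower observed response rate than 6 mg/kg/day

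*Combined protocol and SAP*

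**What the plan says.** Section 9.4.1 states that after the trial "we will select the optimal dose based on isotonic regression as specified in" a cited methods paper. It gives no direction for the monotone constraint. The same paragraph gives as its aim "to increase sensitivity in capturing a nonlinear dose response, we will employ the BOIN design as discussed above".

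Section 9.4.2 picks the dose whose isotonic estimate is closest to the 0.60 target. For ties, "we will select the higher dose level when the isotonic estimate is lower than the target response rate"; if the estimate is at or above target, the lower dose is taken.

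In Section 6.1.2, Table 2 escalates when the number of responses is high and de-escalates when it is low. Its notes add: "When we eliminate a dose, automatically de-escalate the dose to the next lower level". For Part 2, the same section stops 9 mg/kg/day at 0/6, at 1/9 or at 2/12, and treats a low response there as evidence that 6 mg/kg/day was optimal.

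Sections 1.1 and 3 define the optimal dose as the one with the greatest proportion of responders. Section 4.1 hypothesises a dose-response curve that may not be linear. Section 9.3 puts all participants in the analysis sets.

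**The concern.** Isotonic regression forces a monotone curve. Where the data break the imposed order, neighbouring doses are pooled to a common estimate and become tied. The direction therefore decides which doses are pooled, and the tie rule then decides which of the pooled doses is named. Ties are a routine product of this method, not an edge case.

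The parts of the plan assume different directions. Going to a lower dose when response is below target makes sense only if response falls with dose. Going to a higher dose when the estimate is below target makes sense only if response rises with dose. An inverted U does neither.

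At stake is the primary endpoint: the dose named optimal, which informs the planned randomised trial.

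**Working it through.** **Inputs.** 3 mg/kg/day 1/6 and 6 mg/kg/day 4/9 (Section 6.1.2); 9 mg/kg/day x/n, with n up to 15 and stops at 0/6, 1/9 and 2/12 (Section 6.1.2, Table 3 and text); target 0.60, closeness rule and tie rule (Section 9.4.2); all participants kept (Section 9.3).

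**Which direction Table 2 assumes.** I ran the BOIN boundary formulas on non-response with target 0.40 and alternatives 0.6 × 0.40 = 0.24 and 1.4 × 0.40 = 0.56. These multiples are my assumption.

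- Escalate: ln(0.76/0.60) / ln[(0.40 × 0.76)/(0.24 × 0.60)] = 0.316, i.e. response 0.684.
- De-escalate: ln(0.60/0.44) / ln[(0.56 × 0.60)/(0.40 × 0.44)] = 0.480, i.e. response 0.520.

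These are the 0.684 and 0.52 in Section 6.1.2. The escalation counts in Table 2 follow throughout, and the other two rows follow from n = 6. At n = 3 the formula gives a de-escalation limit of 1 and an elimination limit of 0 where the table prints NA. Table 2 is thus BOIN on non-response, with response assumed to fall as dose rises.

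**Part 2 stopping rule.** The exact binomial recursion gives early termination of 90.5, 60.5, 30.5, 11.9 and 3.5% at true rates 0.1 to 0.5. Table 4 prints 90.4, 60.8, 31.0, 11.9 and 3.5%, so the stopping rule is read correctly.

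**Selection.** The method is pool-adjacent-violators weighted by sample size, then the estimate closest to 0.60, then the printed tie rule.

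*Rising fit.* If x/n is below 4/9, 6 and 9 mg/kg/day pool to (4 + x)/(9 + n). At 0/6 this is 4/15 = 0.267, a tie below target, so 9 is taken. At 6/15 it is 10/24 = 0.417, and again 9 is taken. From 7/15 nothing pools. At 11/15 the distances are 0.133 (9 mg/kg/day) and 0.156 (6 mg/kg/day), so 9 is taken. At 12/15 they are 0.200 and 0.156, so 6 is taken.

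*Falling fit.* Because 1/6 is below 4/9, 3 and 6 mg/kg/day pool to 5/15 = 0.333. If x/15 is below 0.333, those two tie below target and 6 is taken. From 5/15 all three share (5 + x)/30. This is below 0.60 up to 12/15 (17/30 = 0.567), so 9 is taken. It is 0.60 or more from 13/15 (18/30), so 3 is taken.

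| 9 mg/kg/day result | Rising | Falling | Highest observed rate |
|---|---|---|---|
| 0/6, 1/9, 2/12, 3-4/15 | 9 | 6 | 6 |
| 5-6/15 | 9 | 9 | 6 |
| 7-11/15 | 9 | 9 | 9 |
| 12/15 | 6 | 9 | 9 |
| 13-15/15 | 6 | 3 | 9 |

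**How often direction alone changes the answer.** Summing the exact probabilities of the reachable results gives:

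| True 9 mg/kg/day rate | 0.3 | 1/3 | 0.4 | 0.44 |
|---|---|---|---|---|
| Probability | 54% | 43% | 24% | 16% |

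Section 6.1.2 anticipates a response of at least one third.

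**Table 5.** In a 20,000-run simulation of its five-dose scenario, starting at dose 3, a rising fit with the printed tie rule selects Dose 3 in about 53% of runs. Table 5 prints 21.8%.

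**The case against.** **Section 6.1.2 already gives the conclusion for early stops.** It eliminates the dose at 0/6 and reads a low non-zero response as pointing to 6 mg/kg/day. This stands as far as it goes, but Section 9.4.2 contains no exception for those results, so the two sections can name different doses. Setting the early stops aside, direction still changes the answer with probability 20% at 1/3 and 8% at 0.44.

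**The cited paper may fix the direction, and 9.4.2 read alone suits a rising fit.** That is possible. But the rising reading is the one that names 9 mg/kg/day on a lower observed rate, and it remains opposed to Table 2.

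**All endpoints are exploratory (Section 4.1), and rates by dose will be visible.** This limits the harm but leaves the primary rule undefined.

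Three stronger readings are tempting but not supported:

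- *The same data can name 3, 6 or 9 mg/kg/day.* For results up to 12/15, an answer of 3 needs the tie rule reversed, and no such rule is in the documents. With the printed rule, 3 appears only at 13/15 or more.
- *Direction flips the answer with probability 80% at a true rate of 1/3.* That is the chance of a result of 6/15 or lower. It is the chance of a flip only if 3 mg/kg/day is left out of the fit, and Section 9.3 keeps all participants.
- *Table 5 was produced with a falling fit.* Its true rates form an inverted U. A falling fit with the reversed tie rule comes closer (17.1/8.5/23.0/18.8/4.0%, against 17.1/9.3/21.8/22.0/1.7% printed) but misses Doses 4 and 5. It also needs a de-escalation limit at n = 3 where Table 2 prints NA. With NA kept, early stopping is about 22.6%, not 28.1%.

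**Conclusion.** The point holds. The documents do not state the direction of the isotonic fit, and Table 2, the tie rule and the inverted-U hypothesis cannot all be met by one monotone fit. With all three doses and the printed tie rule, direction alone decides the selected dose with probability from 54% (true rate 0.3) to 16% (0.44).

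The most natural reading of 9.4.2, a rising fit, contradicts the endpoint definition for every result from 0/6 to 6/15. For the three futility stops it also contradicts Section 6.1.2. A falling fit is no remedy: it also names 9 mg/kg/day at 5/15 and 6/15, and 3 mg/kg/day at 13/15 or more.

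Table 5 does not support the rising reading. What produced its selection row cannot be established from the documents.

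These results assume sample-size weights, Part 1 fixed at its reported counts, and stopping exactly as in Table 3 and its text.

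**What to change.** In Sections 9.4.1 and 9.4.2:

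- Remove the monotone smoothing and base the final selection on the observed response proportion at each dose. Because 1/6 is below 4/9, a unimodal fit with a free peak returns the same three values, so nothing is lost.
- State one tie rule that agrees with the endpoint definition in Sections 1.1 and 3.
- State which doses enter the comparison, since Section 6.1.2 closes 3 and 6 mg/kg/day to further testing while Section 9.3 keeps all participants.
- Settle the criterion. Dropping the smoothing does not do this. With raw proportions, closest-to-0.60 would still pass over 9 mg/kg/day at 12/15 or more (|0.800 − 0.600| = 0.200 against |0.444 − 0.600| = 0.156), although it would then have the greatest proportion responding.
- Reconcile 9.4.2 with Table 2, its notes and the Part 2 stopping text in Section 6.1.2.
- Remove Table 5 ("Operating characteristics of the BOIN design: Part 1") as support for this step, or re-simulate it under the final rule.

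The cost is a wording change and one short simulation. No data collection changes.

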Endpoints:	
Primary Endpoint: Optimal dose of CBD in children and adolescents with ASD, defined as the dose at which the greatest proportion of participants respond in an individualized target symptom domain designated for each individual prior to beginning CBD treatment
 
Secondary Endpoints: Effect sizes of changes in symptoms from baseline of measures developed to assess ASD symptoms, symptoms often associated with ASD, and global functioning
 
Exploratory Endpoints: Effect sizes of changes in MRI signals (i.e., resting-state functional connectivity) from baseline to the final week of treatment

Study Population:	
Sample will include 30 male and female participants with ASD between the ages of 7 and 17 years old. Participants will have fluent speech and an estimated IQ greater than or equal to 80. Individuals of all races and ethnic origins are eligible for participation. Following the completion of the BOIN design, in Part 2 of the trial, we will recruit youth with clinical profiles that most closely resemble youth classified as responders in Part 1 of the trial.

Phase:	
This is a Phase 2 study.

Description of Sites/Facilities Enrolling Participants:	
The study will be conducted at the Child Study Center, Hassenfeld Children’s Hospital, NYU Langone Health.

Description of Study Intervention:	
Study intervention will be 98% pure CBD. The CBD will be Greenwich Biosciences, Inc.’s 100mg/mL oral solution, brand name Epidiolex (V). A Bayesian optimal interval (BOIN) design will be used, such that participants will be assigned to cohorts of size 3 receiving doses of 3, 6, or 9 mg/kg/day, depending on the treatment response of participants in prior cohorts.

Study Duration:	
The duration of the trial is approximately 100 weeks.

Participant Duration:	
Expected duration of subject participation is 8 to 10 weeks, with in-person visits scheduled every other week. Between in-person visits, participants will be contacted via secure email and/or phone to assess for the presence of AE.

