### 4.2 SCIENTIFIC RATIONALE FOR STUDY DESIGN

Suggested dosing to address psychiatric symptoms may be substantially lower compared to dosing in epilepsy studies, which has been the focus of most pediatric CBD research. Further, previous research suggests that CBD has dose-dependent effects on social behavior and anxiety. Therefore, prior to conducting a double-blind trial, identifying optimal dosage is imperative. The BOIN design was employed as our dose finding approach. The BOIN design is flexible and sensitive to nonlinearity, and enables the designation of an optimal dose level based upon the proportion of participants who respond to the treatment.

The BOIN design allowed us to test the intermediate dose (n=9) and the low dose (n=6) and to observe a non-significantly higher rate of response (44%) on the intermediate dose than on the low dose (16%). Based on the overall excellent safety profile in part 1 (all participants completed treatment without any

severe adverse events or need to discontinue treatment) and the suggestion that higher doses of CBD may particularly target striatal D2Rhigh receptors, we have modified the second part of the trial to administer only the still untested 9 mg/kg/day dose, and to focus on participants who present with both ASD and ADHD, as they appear to be the ones most likely to be classified as responders in part 1. This is described in further detail on pages 17-20.

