Given our experience with the first 15 participants, we anticipate that at least 1/3 will be classified as responders. If none of the first 6 participants on 9 mg/kg/day are responders, then we would eliminate the dose and terminate the trial. A low, non-zero response rate, as shown below in Table 3, would also determine terminating the trial, as it would be tantamount to evidence that the optimal dose was 6 mg/kg/day, our initial starting dose.

**Table 3.** Dose elimination rules for cohorts 6 to 10

Cohort	1	2	3	4	5	6	7	8	9	10
Number of participants to be treated at the current dose	3	6	9	12	15	18	21	24	27	30
Dose administered (mg/kg/d)	6	6	3	3	6	9	9	9	9	9
Cumulative N of respondents	1	3	4	4	5	-	-	-	-	-
Terminate if # of responses <=						NA	5	6	7	

Thus, we propose to enroll at least six more participants on the dose of 9 mg/kg/day. If none of them respond, the cumulative number of respondents would remain 5, and we will discontinue the trial; if at least 1 responds within the first 6, we will enroll 3 additional participants. If the total number of responders remains 6, we will discontinue the trial. If the number of responders is 7 or more after 9 participants are enrolled, we will enroll an additional 3 participants for a total of 12 on this dose. If the number of responders does not increase beyond a total of 7, we will terminate due to likely futility.

Table 4 provides the operating characteristics of this design extension for a variety of true response rates.

**Table 4.** Operating characteristics of 9 mg/kg/day evaluation

	Dose 1	Dose 2	Dose 3	Dose 4	Dose 5
True response rate	0.1	0.2	0.3	0.4	0.5
Probability of early termination(%)	90.4	60.8	31.0	11.9	3.5

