#### 9.4.3 ANALYSIS OF THE SECONDARY ENDPOINT(S)

Our secondary objective is to quantify the effect size of changes in a wide range of candidate measures that may reveal response to CBD. Effect sizes and 95% confidence intervals will be reported for all measures obtained at enrollment/baseline and at the final visit (or last observation, in cases of early termination).

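### The primary analysis in 9.4.2 names one optimal dose from isotonic point estimates in groups of 6, 9 and 6 to 15 children, with no interval on any response rate or on the difference between doses

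*Combined protocol and SAP*

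**What the plan says.** The Synopsis defines the optimal dose as "the dose at which the greatest proportion of participants respond". Section 9.4.2 selects by a different criterion: "the dose for which the isotonic estimate of the response rate is closest to the target response rate", with a target of 0.60. Ties are broken by dose level; for example, "we will select the higher dose level when the isotonic estimate is lower than the target response rate". The input is the observed proportion of responders: "As mentioned, response rate will be determined by the proportion of participants classified as responders". Section 9.4.2 plans no confidence or credible interval, no minimum separation, and no way to report that the doses were not separated.

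Section 9.4.3 does plan intervals, for other quantities: "Effect sizes and 95% confidence intervals will be reported for all measures obtained at enrollment/baseline and at the final visit". CGI-I, which defines response, is rated only at the final visit (Schedule of Activities; 8.1). It is therefore outside that sentence, even though Section 3 lists it among the secondary measures.

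Section 6.1.2 reports 1/6 responders at 3 mg/kg/day and 4/9 at 6 mg/kg/day. It plans at least 6 children at 9 mg/kg/day, and 4.3 allows up to 15. Of a low response rate at 9 mg/kg/day, 6.1.2 says that "it would be tantamount to evidence that the optimal dose was 6 mg/kg/day". The same section says that 3 and 6 mg/kg/day have already been excluded from further testing.

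**The concern.** The primary objective is to find a dose to carry into a placebo-controlled trial. The selection rule turns three small proportions into one named dose, and nothing in the primary analysis shows how far the data support that dose over its neighbour. The secondary measures would be reported with intervals and the primary result without one. The sentence in 6.1.2 adds to this, because it reads a futility stop at one dose as support for another. A stop at 9 mg/kg/day adds no new observations at 6 mg/kg/day, where the evidence would still be 4 of 9. A reader planning the next trial could take the named dose as more secure than it is.

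**Working it through.** **Inputs.** 1/6 at 3 mg/kg/day and 4/9 at 6 mg/kg/day (6.1.2). Part 2 stops at 0/6, at no more than 1/9 or at no more than 2/12 on 9 mg/kg/day (cumulative 5, 6 and 7 in Table 3), and otherwise runs to 15. Target 0.60 (9.4.2). The Beta(1,1) priors are an assumption, with Beta(0.5,0.5) as a check.

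**The plan's own figure first.** The probability of early termination is the sum of the three stopping probabilities. At a true rate of 0.1:
- Stop at 6: 0.9^6 = 0.531.
- Stop at 9: P(1 of 6) × 0.9^3 = 0.354 × 0.729 = 0.258.
- Stop at 12: 0.115.

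The sum is 0.905, against 90.4% in Table 4. For true rates 0.1 to 0.5 the recursion gives 90.5, 60.5, 30.5, 11.9 and 3.5%, against the stated 90.4, 60.8, 31.0, 11.9 and 3.5%. This confirms the stopping rule and the possible group sizes of 6, 9, 12 or 15.

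**Precision at each dose** (Clopper-Pearson 95%: lower limit the 2.5% point of Beta(x, n-x+1), upper limit the 97.5% point of Beta(x+1, n-x)):
- 1/6 = 17%: 0.4-64%
- 4/9 = 44%: 14-79%
- 7/15 = 47%: 21-73%
- 9/15 = 60%: 32-84%

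**Separation of doses.** Each rate has an independent Beta(1+x, 1+n-x) posterior, with 1/6 and 4/9 held fixed. The table shows the probability of having the highest of the three rates and the 95% interval for 9 minus 6 mg/kg/day.

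| 9 mg/kg/day result | P(9 highest) | P(6 highest) | 9 minus 6 |
|---|---|---|---|
| 0/6 (stop) | 0.03 | 0.82 | -0.66 to 0.05 |
| 1/9 (stop) | 0.05 | 0.80 | -0.62 to 0.10 |
| 2/12 (stop) | 0.07 | 0.79 | -0.58 to 0.12 |
| 6/15 | 0.37 | 0.54 | -0.40 to 0.32 |
| 7/15 | 0.50 | 0.44 | -0.35 to 0.37 |
| 8/15 | 0.62 | 0.33 | -0.29 to 0.43 |
| 9/15 | 0.74 | 0.23 | -0.23 to 0.48 |
| 11/15 | 0.91 | 0.08 | -0.11 to 0.59 |
| 12/15 | 0.95 | 0.04 | -0.04 to 0.64 |

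With Beta(0.5,0.5) priors, P(9 highest) at 15 children moves by about 0.015 or less. The stops are more sensitive: P(6 highest) becomes 0.86, 0.83 and 0.82, and the 0/6 interval becomes -0.71 to -0.02.

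**What the 9.4.2 rule does with the same data** (raw proportions, no dose removed before selection):
- At 6/15 the observed rate is lower at 9 than at 6 mg/kg/day. The isotonic step pools them to (4+6)/(9+15) = 0.417, and the tie rule names the higher dose.
- At 12/15 the distances to 0.60 are |0.444 - 0.60| = 0.156 and |0.80 - 0.60| = 0.200, so the rule names 6 mg/kg/day although 9 mg/kg/day has the higher rate.

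The probabilities in the table therefore describe the Synopsis criterion, not the selection rule in 9.4.2.

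**The case against.** The documents are candid in several places. Section 4.1 calls every endpoint exploratory, 4.2 describes 44% against 16% as not significantly different, 6.1.2 gives the raw counts, and 9.2 says that no statistical method set the sample size. Anyone can compute an interval from the counts. All of this stands as mitigation, but none of it commits the final analysis to state the uncertainty of the selected dose, and Section 3 words the endpoint as establishing the optimal dose.

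A reader might infer that any result would be close to a coin flip between 6 and 9 mg/kg/day. The figures do not support that: it fits about 6 to 8 of 15. At 11/15 the probability for 9 mg/kg/day is 0.91, and at the futility stops it is 0.79 to 0.82 for 6 mg/kg/day.

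A reader might also infer that the plan must always declare a winner. Section 9.4.2 allows that there may be no optimal dose, and Table 5 shows 28.1% early stopping apart from selection. What is missing is an outcome for completed data that do not separate the doses.

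Finally, a reader might want a probability threshold for using the word optimal. Any such value is a preference. A threshold of 0.80, for example, would be met by 6 mg/kg/day after 0/6 (0.817), which would again turn a futility stop into support for another dose. As shown above, it would also rest on the highest rate, which is not the 9.4.2 criterion.

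**Conclusion.** The point holds in this form: the primary analysis reports a single dose from point estimates whose exact 95% intervals span roughly 50 to 65 percentage points, with no interval on any rate or difference. For mid-range results at 9 mg/kg/day the data barely separate it from 6 mg/kg/day.

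The intervals for single doses need only the counts and binomial sampling. The comparative figures also assume independent Beta priors and no constraint on the shape of the dose-response curve.

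All of them capture sampling error only. Part 2 requires ASD with ADHD, the profile of all five Part 1 responders (6.1.2), so the 9 and 6 mg/kg/day groups differ in population as well as dose. No interval repairs that. The gap is worth closing before the final analysis. It does not invalidate the design, and nothing here says which dose is right.

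**What to change.** In 9.4.2:
- Report n/N with an exact 95% confidence interval for each dose.
- Report a 95% interval for the 9 minus 6 mg/kg/day difference, with its method fixed in advance. The choice matters at the margin: after 0/6 the two priors above disagree on whether zero is included.
- Call the selected dose a candidate dose, and state that the doses were not distinguished when that interval includes zero.
- Label every comparison of Part 1 with Part 2 as confounded by the change of population.

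In 6.1.2, reword the sentence on a low response so that a stop is reported as futility at 9 mg/kg/day and not as evidence that another dose is optimal.

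The sponsor should also reconcile three statements: greatest proportion (Synopsis, Section 3), closest to the target (9.4.2), and the exclusion of 3 and 6 mg/kg/day (6.1.2). Any posterior probability should wait for that and use the criterion that results.

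The cost is a few lines of text and minutes of analysis on data already being collected. The downside is a less definite primary conclusion. With Beta(1,1) priors the difference interval still includes zero at 12/15, so the sponsor should expect to report that the doses were not distinguished across most of the range.

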### 3 OBJECTIVES AND ENDPOINTS

OBJECTIVES	ENDPOINTS	JUSTIFICATION FOR ENDPOINTS
Primary		
Determine the optimal dose of CBD in children and adolescents with ASD	Establishment of optimal dose of CBD in children and adolescents with ASD, defined as the dose at which the greatest proportion of participants respond. Discussed further in the Dosing and Administration section, the definition of treatment response will be individualized for each participant based upon a predetermined target symptom cluster.	Identification of the optimal dose of CBD (within the range tested) is desirable given the insufficient research in this area and the potential for dose-dependent inverted-U effects (2, 9).
Secondary		
Identify the primary outcome measure for a subsequent double-blind placebo-controlled RCT	Change in core and associated symptoms from baseline based upon measures developed to assess ASD symptoms, symptoms often associated with ASD, and global functioning including: 
 
- ABC Social Withdrawal and Irritability Subscales
 
- ASC-ASD-Child and Parent
 
- AFEQ
 
- ADAMS
 
- BIS
 
- CGI-I
 
- CGI-S
 
- HSQ-ASD
 
- OSU Autism CGI Severity
 
- OSU Autism CGI Improvement
 
- RBS-R
 
- SCARED
 
- SDSC
 
- SRS-2
 
- SWAN (Part 2 of the trial)
 
- Vineland-3
 
	Measures were selected because they have been widely used in prior trials in ASD (ABC, CGI, HSQ-ASD, OSU Autism CGI, RBS-R, SCARED, SRS-2, SWAN [Part 2], Vineland-3), or have been used in a recent trial of CBD in Fragile X syndrome (ADAMS) or have been used in medication trials more broadly (SDSC), or represent new and innovative tools available in the ASD field (ASC-ASD; AFEQ; BIS).
Tertiary/Exploratory		
Assess underlying brain mechanisms using MRI	Change in brain activity, indexed by resting-state functional connectivity. Otherwise, results will be reported	Inform the feasibility of incorporating biomarkers (e.g., resting-state functional

OBJECTIVES	ENDPOINTS	JUSTIFICATION FOR ENDPOINTS
	qualitatively (conducted at in-person visits only, if participants agree)	connectivity) in our future studies and potentially yield testable hypotheses.

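### Section 9.4.2 claims a high probability of selecting the true optimal dose, but its own Table 5 shows 21.8%, for five doses rather than the trial's three

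*Combined protocol and SAP*

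**What the plan says.** Section 9.4.2 chooses the optimal dose after the trial as "the dose for which the isotonic estimate of the response rate is closest to the target response rate", with a target of 0.60. Section 3 describes the same endpoint as the optimal dose "defined as the dose at which the greatest proportion of participants respond", and the Synopsis (1.1) agrees.

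The section then introduces its performance evidence: "Table 5 shows the operating characteristics of a 5-dose BOIN design based on 1000 simulations". The next sentence draws the conclusion: "The operating characteristics show that the design selects the true optimal dose, if any, with high probability". It adds that allocation favours the doses whose response rates are closest to 0.6. The table is titled "Operating characteristics of the BOIN design: Part 1" and contains one scenario.

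The trial itself has cohorts "receiving doses of 3, 6, or 9 mg/kg/day" (Synopsis), and Section 6.1.2 says: "Participants in the first cohort were treated at Dose Level 2". The start dose of the simulation behind Table 5 is not given.

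**The concern.** The text draws a conclusion that the table beside it contradicts. Table 5 is the only place in the protocol that shows how often the primary-endpoint method finds the right dose. The study exists to choose a dose and an outcome for a later placebo-controlled trial. A reader who relies on the sentence would think the selection method dependable, although the only evidence offered does not show that.

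The evidence is also for a different design: five doses instead of three, with an unknown start dose. Table 4 in Section 6.1.2 does not fill the gap, because it reports only early-termination probabilities for the 9 mg/kg/day evaluation.

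**Working it through.** **Inputs, all from Table 5 (1000 simulations, target 0.60)**

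| | Dose 1 | Dose 2 | Dose 3 | Dose 4 | Dose 5 | Early stopping / total |
|---|---|---|---|---|---|---|
| True rate | 0.40 | 0.50 | 0.60 | 0.55 | 0.45 | |
| Selected, % | 17.1 | 9.3 | 21.8 | 22.0 | 1.7 | 28.1 |
| Mean treated | 5.84 | 4.39 | 10.55 | 5.36 | 0.86 | 27 |

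**Is the table intact?** Selection: 17.1 + 9.3 + 21.8 + 22.0 + 1.7 = 71.9, and 71.9 + 28.1 = 100.0. Participants: 5.84 + 4.39 + 10.55 + 5.36 + 0.86 = 27.00, which matches the stated 27. The columns are not misread, and early stopping means that no dose was selected.

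**Which dose is the true optimum?** Dose 3, under both definitions: it sits exactly at 0.60 and has the highest true rate.

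**How often is it selected?**

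- All runs: 21.8%. Standard error = √(0.218 × 0.782 / 1000) = 1.31 points; 95% interval 19.2 to 24.4%. It is missed in 100 − 21.8 = 78.2% of runs.
- Dose 3 minus Dose 4: 21.8 − 22.0 = −0.2 points. Multinomial standard error = √((0.218 + 0.220 − 0.002²) / 1000) = 2.09 points; interval −4.3 to +3.9. The two doses cannot be told apart, so Dose 3 is selected no more often than Dose 4, but one cannot say less often.
- Doses with true rates of 0.40 to 0.50 (Doses 1, 2 and 5): 17.1 + 9.3 + 1.7 = 28.1%. That this equals the no-selection figure is a coincidence.

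**More generous readings**

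- Only runs that select a dose: 21.8 / 71.9 = 30.3% (719 runs, standard error 1.71 points, interval 27.0 to 33.7%). A random pick among five would give 20%. The method does better than that but is wrong about seven times in ten.
- Dose 4 also counted as correct: 21.8 + 22.0 = 43.8% of all runs (standard error 1.57 points, interval 40.7 to 46.9%).
- Both concessions together: 43.8 / 71.9 = 60.9%.

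**Allocation.** Dose 3 does receive the most participants (10.55 of 27), and Doses 3 and 4 together receive 15.91 (58.9%). But Dose 1, the furthest from target, receives 0.48 more than Dose 4 (5.84 against 5.36), so this half of the sentence is only partly supported.

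**Could Table 5 be reproduced?** Not exactly, because neither the start dose nor the direction of the isotonic fit is stated. The closest simulation used the Table 2 boundaries, a start at Dose 3, active rules at n = 3, and response non-increasing in dose, as the escalation rule implies. It selected Dose 3 in about 24%, with about 30% early stopping. With that direction of fit, no start dose or rule variant tried took Dose 3 above about 33%.

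**Would three doses rescue the sentence?** Illustrative runs with a start at Level 2, a maximum of 30 and the same direction of fit gave correct selection from 11 to 14% (assumed true rates 0.4/0.5/0.6) up to 53 to 60% (0.6/0.5/0.4). With an increasing fit the range was about 5 to 63%. These true rates are assumptions, not protocol figures.

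**The case against.** The strongest objection is that Table 5 cannot both fail to describe the three-dose trial and prove that trial's method unreliable. This stands as a limit on the conclusion. The table shows weak selection in one difficult five-dose scenario; for the three-dose design it shows only that the claim has no support.

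Second, Dose 4 at 0.55 lies inside the 0.52 to 0.684 uncertainty interval of Section 6.1.2, so the design does not aim to move away from it. That is a fair reason to report the combined figure, but 43.8% is still under half, and the sentence speaks of the one true optimal dose.

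Third, Section 9.4.2 openly calls the simulated design a five-dose one. It does, so nothing is concealed. The table title, however, still presents it as Part 1 performance.

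Fourth, the table might be what is wrong, and the sentence right. An increasing isotonic fit gives about 50 to 58% for Dose 3 in the five-dose case, but that selection pattern does not match the printed one. The table adds up and is plausible; confirming the simulation settings before editing is sensible.

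Last, the consequence is small. Section 4.1 calls all endpoints exploratory, Part 1 is complete, and cohorts 6 to 10 follow Table 3. That limits the stakes. It does not make the sentence correct, and Section 9.4.1 still plans isotonic dose selection at the end of the trial.

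**Conclusion.** The concern holds. The sentence claims high probability; the table gives 21.8% for the true optimal dose, 22.0% for the next-best dose and 28.1% for no selection. The single generous readings give 30.3% or 43.8%. Only both concessions together reach 60.9%, and that is no longer the quantity the sentence describes. The conclusion needs nothing beyond the printed table and does not depend on re-simulating it.

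The documents give no selection performance for three doses starting at Level 2, so the reliability of the dose choice in this trial is unquantified. The error is one of reporting on the primary-endpoint method. It should be fixed, but it changes no analysis and no remaining dosing or stopping decision.

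**What to change.** In Section 9.4.2, delete the high-probability claim and state the results: optimal dose selected in 21.8% of runs, Dose 4 in 22.0%, no dose in 28.1%. Retitle Table 5 as a single-scenario illustration of a five-dose design, not the three-dose design that was run. State its start dose and the direction of the isotonic fit, after checking both against the original simulation. Do not cite the table as evidence that the dose selection is reliable. Adjust the allocation wording to say that Dose 3 receives the most participants, while Dose 1 receives slightly more than Dose 4.

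A three-dose simulation from Level 2 over several scenarios would be informative but is optional. The required change is one sentence, with its allocation clause, and one table label; its only cost is that the stated performance becomes less favourable.
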